Objectives	
Primary overall objective is to test closed loop real time fMRI neurofeedback that specifically targets our hypothesized attentional mechanism of depression (i.e., neural perseveration of negative states) to reduce depression severity.
 
The primary objective in the R61 phase is to compare the time spent in the most negative state before and after real-time neurofeedback training, comparing active vs sham training. The secondary objective is to determine the lowest # of sessions necessary.
 
The primary objective of the R33 phase in a randomized controlled trial is to compare active an sham feedback on depression outcome and to determine the relationship between changes in neural perseveration and change in depression.

Number of Subjects	R61 Phase – 60 patients with MDD expected to enroll. R33 Phase (if approved) – 80 patients with MDD expected to enroll.

CONFIDENTIAL

Main Inclusion and Exclusion Criteria	
Inclusion:
 
• gender, inclusive• adult aged 18 – 65• meets Diagnostic and Statistical Manual of Mental Disorders (DSM-5) criteria for MDD according to the Clinician-Administered MDD Scale for DSM-5 (unipolar depression or bipolar II depressed)• scores at least a minimum score of 16 on Montgomery Asberg Depression Rating Scale (MADRS)• normal cognition• participants must be able to read and understand English• participants must be able to provide consent 
Exclusion:
 
• pregnancy (female participants)• outside age range• MRI contraindications (medical implant, claustrophobia, etc.)• use of psychoactive medication (including antidepressants) or currently in therapy• neurological disorder or any condition that in the view of the PI could impact brain data, cause depression, require medication that could cause depressive symptoms, or otherwise result in participant being unfit for study (for example, co-morbid psychotic disorders, neurological disorders, developmentally or cognitively disabled/impaired, active alcohol or drug abuse/dependence within the past 6 months)• non-English speaking• non-correctable vision loss• refusal to provide informed consent• representing an active suicide risk
Intervention	Behavioral intervention (neurofeedback)
Statistical Methodology	Linear mixed effects regression modeling will be used to assess changes in neural perseveration and MADRS over time in the active neurofeedback group. Multiple linear regression will be used to assess the relationship between reduced neural perseveration and reduced MADRS scores. Two-sample t-tests will assess group differences in task performance and symptoms after each session of treatment in order to determine the necessary dose of neurofeedback for reducing neural perseveration.

CONFIDENTIAL

Data and Safety Monitoring Plan	We have elected to utilize a Data and Safety Monitoring Board as part of our data and safety monitoring plan.
--	---

Background and Study Rationale

This study will be conducted in full accordance with all applicable University of Pennsylvania Research Policies and Procedures and all applicable Federal and state laws and regulations.

1 Introduction

Depressed individuals process negative stimuli differently from healthy participants, leading to differences in attention, memory, and cognitive control (Mogg and Bradley 2005, Mogg, Field et al. 2005, Gotlib and Joormann 2010, Sanchez, Vazquez et al. 2013, Snyder 2013, Jones and Sharpe 2017, Koster 2017). Depressed participants also tend to show larger and more prolonged neural responses to negative stimuli (Disner, Beevers et al. 2011). Relatedly, other studies have found that depressed individuals specifically have difficulty in disengaging from negative stimuli (Armstrong and Olatunji 2012, Sanchez, Vazquez et al. 2013, Mennen, Norman et al. 2019). This inability to transition out of negative states may manifest clinically as rumination--the automatic, perseverative replay of negative thoughts (Gotlib 1982, Nolen-Hoeksema, Wisco et al. 2008).

Behavioral training has been the main approach to reduce attentional biases in depression, yet behavioral measures such as button presses and eye movements are downstream effects of underlying neural differences. Neural feedback, such as from functional magnetic resonance imaging (fMRI), allows for measures that are “closer to the source” of the biases, and thus have the potential to be more sensitive and informative. Indeed, depressed participants can show enhanced neural processing of negative stimuli that are presented quickly even in the absence of any indication from behavior (Fales, Barch et al. 2008, Suslow, Konrad et al. 2010, Victor, Furey et al. 2010). We therefore seek to combine the advantages of adaptive feedback with the potentially enhanced sensitivity of neural measurements of attention.

1.1 *Background and Relevant Literature*

Depression is one of the most prevalent, chronic and debilitating illnesses; it affects 10% of individuals within the past 12 months (Hasin, Sarvet et al. 2018) and is the leading cause of disability world-wide (Kessler, Aguilar-Gaxiola et al. 2009, Collins, Patel et al. 2011). Effective pharmacotherapies are available but produce responses in only approximately half of patients ((APA 2013); STAR-D) and following nonefficacy with an initial SSRI, only about 20% remit (Rush, South et al. 2020). Thus, finding additional treatment strategies to achieve better treatment outcome is highly desirable.

CONFIDENTIAL

In this R61/R33 proposal we will test the efficacy of a new psychotherapeutic strategy, closed loop real time fMRI neurofeedback, in reducing negative attention bias and depressive symptoms. This is the first real time feedback therapy to use the person's brain state (based on all of the person's brain signal) for cloud based machine learning decoding and feedback rather than the more typical approach of conveying feedback through a separate gauge or scale. It is well established that depressed individuals have accentuated processing of negative stimuli, leading to differences in attention, memory, and cognitive control (M1-5) and more prolonged neural responses to negative stimuli (6), manifesting clinically as rumination (M1, 7). Neural feedback from functional magnetic resonance imaging (fMRI), provides measures that are "close to the source" of the biases, with the potential to be sensitive and informative. In a pilot study (Mennen et al, BP 20) we adapted a closed loop procedure and showed feasibility data for reducing neural measures of negative attention bias that was correlated with reductions in depressive symptoms.

Thus, this project will establish real-time fMRI neurofeedback as a means of reducing attention to negative stimuli by reducing neural perseveration of negative states as a treatment for MDD. Results from this line of research will inform feedback strategies and improve understanding of neural mechanisms underlying negative attention and MDD.

2 Study Objectives

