- For a one-sample t-test with a two-sided alternative and type I error rate of 5%, 36 participants per arm will yield 80% power for a Cohens $d = 0.53$ or larger, which is sufficient to detect the effect size of 0.93 Visit 1 to post-treatment MADRS score decrease in the pilot data (**Hypothesis 1**). For a two-sample t-test with a two-sided alternative and type I error rate of 5%, 36 participants will yield 80% power for a Cohens $d = 0.74$ or larger. **Hypothesis 2** will utilize Pearson correlation between change in MADRS and change in negative attention scores. If nonlinearity is detected, we will employ a Spearman correlation analysis. A sample size of n=36 corresponds to 80% power to detect a significant (at 5% alpha level) correlation as low as $r=0.45$, which is sufficient to detect the effect size of $r=0.48$ found in the pilot data (**Figure 1**). **Hypothesis 3** will use a two-sample t-test comparing real vs sham NF. Pilot study data indicated a change in MADRS from baseline to 3 month follow-up corresponding to Cohen's $d=0.95$. A two-sample t-test, with 36 per group, at 5% significance level, gives 80% power to detect $d=0.74$ or larger.

CONFIDENTIAL

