6.2 Statistical Methods

Statistical analysis will be performed using the R statistical environment assuming 5% type I error rates. Linear mixed effects regression modeling (using the lme4 R package) will be used to assess evidence of reduced neural perseveration and reduced MADRS over time in the active neurofeedback group. Two-sample t-tests will be used to compare differences in neural perseveration and MADRS scores between the active neurofeedback and sham (yoked) neurofeedback groups after each additional session of treatment in order to establish the lowest dose of training necessary to significantly reduce neural perseveration. We will utilize multiple linear regression to assess the relationship between reduced perseveration and the reduction of MADRS scores in the active neurofeedback group while accounting for various confounds.

6.3 Control of Bias and Confounding (if applicable, typically observational study or if randomization is not taking place)

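### The documents do not consistently name one R33 primary test; error is 5% if only the between-arm MADRS test counts, but about 10% to 14% if any significant result did

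*Combined protocol and SAP*

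**What the plan says.** Several places bear on what R33 is primarily testing, and they differ.

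- **Study Summary, Objectives.** The primary objective of R33 "is to compare active an sham feedback on depression outcome and to determine the relationship between changes in neural perseveration and change in depression". That is two questions under one primary label.
- **Section 3.4.1.** The primary endpoint is change in negative attention bias. The same paragraph says that R33 concentrates on depressive severity.
- **Sections 2.2 and 3.4.2.** All three R33 aims (active versus sham, relationship, durability) stand under headings for secondary objectives or endpoints.
- **Section 5.1.** MADRS is called the primary outcome measure.
- **Section 6.1.** The label Hypothesis 1 closes a sentence on a one-sample test of the decrease in MADRS from Visit 1 to post-treatment. The two-sample sentence that follows has no label. Hypothesis 2 is the correlation between change in MADRS and change in negative attention. Hypothesis 3 is active versus sham, justified by pilot MADRS change from baseline to 3-month follow-up.
- **Section 6.3.2.** The analysis of the primary outcome is a two-sample t-test of active versus sham on MADRS. No phase, visit or definition of change is given.

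On error rates, section 6.2 plans all analysis "assuming 5% type I error rates". Section 6.1 repeats this for Hypothesis 2 ("A sample size of n=36 corresponds to 80% power to detect a significant (at 5% alpha level) correlation") and Hypothesis 3 ("A two-sample t-test, with 36 per group, at 5% significance level"). No section gives a testing order, a split of alpha, or a rule on whether one or both parts of the objective must succeed.

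**The concern.** R33 is the efficacy phase. With no single primary test and no success rule, a result other than the active-sham comparison could be reported as meeting the primary objective.

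Two routes matter most. Section 6.2 assesses the relationship between perseveration and MADRS within the active group only, and n = 36 in section 6.1 is one arm's expected completers. Such a correlation can be real when treatment does nothing relative to sham. The Hypothesis 1 label, taken literally, belongs to a pre-post change that says nothing about sham at all. A follow-up difference could also be presented as durability when no post-training effect had been shown.

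**Working it through.** **1. Reproduce the plan's R33 power figures.** Inputs from section 6.1: 36 per arm, two-sided 5%, 80% power. The t-tests use the noncentral t distribution.

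- Two-sample: noncentrality = d × √(n/2) = 0.74 × √18 = 3.14. Power at the written 5% is 87.2%, against the plan's statement that "36 participants will yield 80% power for a Cohens $d = 0.74$ or larger". At 5%, 80% power is reached at d = 0.67.
- One-sample: noncentrality = d × √n = 0.53 × 6 = 3.18. Power at 5% is 87.1%, against "36 participants per arm will yield 80% power for a Cohens $d = 0.53$ or larger". At 5%, 80% power is reached at d = 0.48.
- At two-sided 2.5%, 80% power is reached at d = 0.740 (two-sample) and d = 0.533 (one-sample). These match the plan's figures.
- Correlation (Fisher z): atanh(0.45) × √33 − 1.96 = 0.82, so power is 79.5%. The plan's r = 0.45 reproduces at 5%. Power at the pilot r = 0.48 is about 85%.
- R61 for comparison, 27 per arm: the two-sample d = 0.86 matches 2.5% (5% gives 0.777), whereas the one-sample d = 0.56 matches 5%.

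**2. Error rate under each reading, at the written 5%, with every null true.**

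- Only the section 6.3.2 test supports the primary claim: 5%.
- Both parts of the Study Summary objective must succeed: at most 5% for the joint claim.
- Either part suffices, tests independent: 1 − 0.95² = 9.75%.
- Any of three tests suffices (active versus sham post-training, relationship, active versus sham at follow-up), all independent: 1 − 0.95³ = 14.3%.

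**3. Allow for correlation between the two MADRS tests.** The documents give no value, so a range is assumed and the relationship test is kept independent. With q the chance that at least one MADRS test rejects (bivariate normal), the three-test error is 1 − 0.95 × (1 − q).

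| Assumed correlation | q | Any of three |
|---|---|---|
| 0 | 9.75% | 14.3% |
| 0.5 | 9.07% | 13.6% |
| 0.7 | 8.35% | 12.9% |
| 0.9 | 7.04% | 11.7% |

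**4. If the t-tests were really meant at 2.5%** and the correlation at 5%: two tests give 1 − 0.975 × 0.95 = 7.4%; three independent tests give 1 − 0.975 × 0.95 × 0.975 = 9.7%.

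**5. Hypothesis 1 read literally as the pre-post test.** Suppose neurofeedback adds nothing over sham, but patients improve non-specifically by an assumed standardised 0.2, 0.3 or 0.5. A one-sample test on 36 patients at 5% then rejects 21%, 42% or 83% of the time. The rates in steps 2 to 4 do not cover this case.

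**The case against.** The strongest reply is that the plan already has a primary test. Section 6.3.2 names active versus sham on MADRS, section 5.1 calls MADRS the primary outcome measure, and section 3.4.1 points R33 at depressive severity. On that reading the primary claim carries 5% error. The relationship is a mechanistic question that need not share an error family with efficacy, and no section calls a significant correlation an efficacy success.

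Much of this stands. A reader might infer that R33 has a false-positive rate of 10% to 14%. The documents do not support that as a plain statement. It needs every null to be true and any single significant result to count as a claim, and the plan says neither. The word joining the two parts of the Study Summary objective could equally mean that both must succeed.

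The reply still does not settle which test is primary. Section 6.3.2 gives no phase or visit. Section 3.4.1 names a different primary endpoint in the same paragraph. The secondary headings cannot demote the relationship without also demoting active versus sham, which is listed beside it. The Study Summary still calls the relationship primary.

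A reader might also take the match at 2.5% as proof of an undisclosed alpha split. It is not: the R61 one-sample figure matches 5%, and a plain error in the effect sizes is equally possible.

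**Conclusion.** The supportable finding is an inconsistency. The Study Summary and sections 2.2, 3.4.1, 3.4.2, 6.1 and 6.3.2 do not agree on one R33 primary test, and no rule says how the other tests may be used. The consequence is conditional: 5% if section 6.3.2 governs; about 10% if either part of the Study Summary objective suffices; about 12% to 14% if any of the three tests does. The last two figures assume all nulls true and per-test alpha of 5%, and the range reflects the assumed correlation of 0.9 to 0. They do not count the mixed-model and per-session tests in section 6.2.

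This should be corrected before R33 starts. It does not show that the active-sham MADRS test is itself invalid. The documents also do not dictate an order between relationship and durability: the Study Summary makes the first primary and omits the second.

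**What to change.** - Name active versus sham on MADRS at the post-training visit as the sole R33 primary test, at two-sided 5%.
- In section 6.1, relabel Hypothesis 1 as that between-arm test. This is a real change of label, since the text now attaches it to the one-sample decrease.
- Align the Study Summary and sections 2.2, 3.4.1, 3.4.2 and 6.3.2 with this, adding the phase and visit to section 6.3.2.
- State that the relationship and follow-up tests are secondary and cannot support an efficacy or durability claim unless the primary test is significant. The order between them is the sponsor's choice, but it should be written down: if both were tested at 5% with no order after a true primary effect, the error over the pair could again reach 1 − 0.95² = 9.75%.
- Reconcile the follow-up time point for Hypothesis 3. Section 6.1 cites 3-month pilot data, sections 4.1 and 5.2.4 describe one follow-up at one month, and section 5 describes two within 3 months.
- Reconcile the alpha behind d = 0.74 and d = 0.53: either state 2.5%, or restate them as 0.67 and 0.48 at 5%.

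The cost is a short statistical paragraph and edits to a few sentences. No extra patients are needed, because the primary test keeps the full 5%. The downside is that the relationship and follow-up results are exploratory if the primary test fails. Keeping both parts of the objective primary by splitting alpha to 2.5% each would hold the error at 1 − 0.975² = 4.94%. It would move 80% power to d = 0.74 and r = 0.49, and leave 78% power at the pilot r = 0.48. R33 proceeds only if R61 succeeds, so there is time to settle this.

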2.1 Primary Objective

The overall objective of this R61/R33 is to test whether closed loop real time fMRI neurofeedback that specifically targets our hypothesized attentional mechanism of depression (i.e., neural perseveration of negative states) reduces depression severity. This study will be the first dose-finding test of real-time fMRI effect on negative attention bias.

2.2 Secondary Objectives (if applicable)

Phase R61:

- Aim 1: Target Engagement. Response to real-time vs sham neurofeedback will be determined by pre-post change in selective attention to negative stimuli.
- Aim 2: Determine the lowest "dose" of training necessary to reduce selective attention to negative stimuli.
- Exploratory Aim: Examine behavioral perseveration on negative stimuli.

Phase R33 will be conducted only if Phase R61 is successful:

- Aim 1: Conduct a randomized controlled trial (RCT) to compare the effect of real-time neurofeedback vs. sham on depression outcome in patients with MDD.
- Aim 2: Determine the relationship between the markers of neural perseveration established in the R61 phase and the reduction in depressive symptoms.
- Aim 3: Determine the durability of the treatment effect.

3 Investigational Plan

CONFIDENTIAL

Following ascertainment of inclusion and exclusion criteria and consent, participants will be enrolled and randomized to either the active or sham group. In subsequent daily visits, they will perform the gaze task and receive neurofeedback training. In general, it is expected that the visits will occur on sequential days, except for weekends, but there will be flexibility for patient schedule. Participants will also complete 2 follow-ups. See below for visit breakdown.

- R61 phase will include:
 - 1 pre-training session (includes screening)
 - 4 training sessions (the first session includes a baseline MRI scan)
 - 1 post-training session
 - 2 follow-up sessions
- R33 phase will include:
 - 1 pre-training session (includes screening)
 - training sessions (number of sessions will be determined in the R61 phase)
 - 1 post-training session
 - 2 follow-up sessions

3.1 General Design

This study uses neurofeedback to target neural mechanisms underlying attentional bias in participants with major depressive disorder (MDD), with the goal of evaluating whether this intervention can be used to reduce the negative attentional bias.

Following random assignment, participants will begin the protocol with either active neurofeedback or sham (yoked) neurofeedback.

3.2 Allocation to Interventional Group

Participants will be randomly assigned to treatment with active neurofeedback or sham. At the end of the initial assessment, a computer-generated random number list will be used to allocate participants to the two treatment conditions.

3.3 Study Measures

Sources of data includes fMRI data from MRI scanner, clinical evaluations (diagnoses, observer ratings), and behavioral gaze data.

In the R61 phase we will compare cloud based real time fMRI feedback with placebo (sham feedback) in reducing negative attention bias and depressive symptoms. This study will be the first dose-finding test of real-time fMRI effect on negative attention bias. Measures include:

- Structured Clinical Interview for DSM-5 (SCID)
 - Clinician-administered diagnostic exam
 - Completed during pre-training session for screening and eligibility assessment
- Montgomery Asberg Depression Rating Scale (MADRS)
 - Clinician-administered scale used to assess the severity of depression

CONFIDENTIAL

- Obtained during pre-treatment session (for screening and eligibility assessment), 3 training sessions, post-training session, and 2 follow-up sessions
- State-Trait Anxiety Inventory (STAI)
 - Self-report questionnaire used to measure types of anxiety
 - Obtained during pre-treatment session, 3 training sessions, post-training session, and 2 follow-up sessions
- Mood and Anxiety Symptom Questionnaire (MASQ)
 - Self-report questionnaire used to measure mood symptoms
 - Obtained during pre-treatment session, 3 training sessions, post-training session, and 2 follow-up sessions
- Negative perseveration during a go/no-go task
 - Go/no-go task with overlaid face/scene stimuli; brain response triggers next stimulus
 - Obtained in 3 training sessions and post-training session
- Negative gaze
 - Negative gaze collected in gaze data following each real time fMRI feedback session
 - Obtained during 3 training sessions and post-training session

In the R33 phase we will compare the effect of real-time neurofeedback vs. sham on depression outcome in patients with MDD. The number of training sessions will be determined in the R61 phase.

- Structured Clinical Interview for DSM-5 (SCID)
 - Clinician-administered diagnostic exam
 - Completed during pre-training session for screening and eligibility assessment
- Montgomery Asberg Depression Rating Scale (MADRS)
 - Clinician-administered scale used to assess the severity of depression
 - Obtained during pre-treatment session (for screening and eligibility assessment), 3 training sessions, post-training session, and 2 follow-up sessions
- State-Trait Anxiety Inventory (STAI)
 - Self-report questionnaire used to measure types of anxiety
 - Obtained during pre-treatment session, 3 training sessions, post-training session, and 2 follow-up sessions
- Mood and Anxiety Symptom Questionnaire (MASQ)
 - Self-report questionnaire used to measure mood symptoms
 - Obtained during pre-treatment session, 3 training sessions, post-training session, and 2 follow-up sessions
- Negative perseveration during a go/no-go task
 - Go/no-go task with overlaid face/scene stimuli; brain response triggers next stimulus
 - Obtained in training sessions and post-training session, although exact number will be determined in R61 phase

3.4 Study Endpoints

3.4.1 Primary Study Endpoint

Our primary aim to test the efficacy of the closed loop real time fMRI neurofeedback: does this neurofeedback that specifically targets our hypothesized attentional mechanism of depression (i.e., neural perseveration of negative states) lead to reduced depression severity? The primary endpoint would then be a change in negative attention bias following training visits. Phase R61 will focus on this negative attention bias, and Phase R33 will focus on change in depressive symptom severity.

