3.4.2 Secondary Study Endpoints

Phase R61:

- Aim 1: Target Engagement. Response to real-time vs sham neurofeedback will be determined by pre-post change in selective attention to negative stimuli. Following behavioral and symptom assessment participants will receive 3 training sessions conducted in the fMRI scanner, during which participants will view overlaid neutral scenes and negative faces while attending to the scenes. Multivariate pattern analysis will quantify attention to the scenes vs. faces in real-time using a cloud-based framework that adjusts each subsequent image to reward or punish based on attention to the current image. Feedback will be delivered by changing the opacity of the images of the scene target vs face distractor. We have identified a potential neural locus of the negative attentional bias — the inability of MDD to escape from a brain state in which they are attending to negative face distractors even though task irrelevant, what we refer to as “neural perseveration” (higher conditional probability of staying in the same negative state vs. healthy individuals).
- Exploratory aim: Behavioral perseveration on negative stimuli. In addition to a neural target we will also explore a behavioral perseveration target using a gaze task (R61 Exploratory Aim). In that task, patients view a screen with positive, neutral and negative images. Using an eye-tracker, the amount of time that participants spend looking at negative stimuli after first fixating on those stimuli will be recorded and compared. To further support the hypothesis that understanding negative perseveration is relevant to brain mechanisms in depression, we will measure the same probability at the end of each day of neurofeedback treatment. The progressive change over time will provide further comparisons in the active vs sham groups.
- Aim 2: Determine the lowest “dose” of training necessary to reduce selective attention to negative stimuli. Neural and behavioral markers obtained after each session will be used to determine the lowest number of sessions that produce a significant effect, which will be chosen for the R33 phase.

R33 Phase:

- Aim 1: To conduct a randomized controlled trial (RCT) to compare the effect of real-time neurofeedback vs. sham on depression outcome in patients with MDD.
- Aim 2: To determine the relationship between the markers of neural perseveration established in the R61 phase and the reduction in depressive symptoms. Neural

CONFIDENTIAL

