Yes No

The following are examples of procedures involving ionizing radiation:

(Review [appendix 15.3](#) and [appendix 15.5](#))

- X-rays (examples: CT scan, chest x-ray, hand/wrist x-ray, abdomen x-ray, DEXA, pQCT, Fluoroscopy/Angiography)
- Nuclear Medicine scans (examples: FDG-PET, PET/CT, Tc-99m, SPECT, MUGA, bone scan)
- If you are unsure please contact [name] in EHRS ([contact]).

Ultrasound

Yes No

If yes, there is no protocol specific language to include but please contact [name] at: [contact]

Will your study be using CT Scans? (CACTIS is the appropriate contact for studies involving CT scans)

Yes No

Studies involving Nuclear Medicine: Will subjects be undergoing any of the following procedures specific to research:

MUGA

(See Nuclear Medicine-Muga Scan)

PET/CT Scan

(See PET/CT Scan)

Bone /DXA

(See Bone Scan)

Check off all of the following procedures that will be performed in your research- each option you select will link to the template language document:

Apheresis/plasma exchange

CONFIDENTIAL

- [Leukapheresis](#)
- [Bone Marrow Biopsy or Aspirate](#)
- [Use of AP clinical specimens](#)
- [Biopsies- check those which apply](#)
- [Blood draw](#)

5.1 *Pre-Training Visit*

The pre-training visit will include screening procedures.

Participants will be recruited, consented, and evaluated. They will also complete MRI safety screening forms and self-report medical history. This includes completing informed consent. Each patient's medical history is reviewed by [name] and, when clinically indicated, a physical examination and appropriate laboratory tests will be obtained to ensure that patients are diagnostically eligible. Consenting patients will be diagnosed with the Structured Clinical Interview for DSM-5. Participants who meet eligibility requirements will be screened using the MADRS, which will be the primary outcome measure and will have a minimum score of 16. Participants will also complete the STAI & MASQ.

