6.3.2 Analysis of Primary Outcome of Interest

We will use a two-sample t-test comparison of active neurofeedback vs sham to determine the effect on MADRS scores.

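### R61 has no designated primary test: MADRS is called primary without being limited to R33, and the neural endpoint has two operational descriptions and no named contrast

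*Combined protocol and SAP*

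**What the plan says.** **Endpoint by phase.** Section 3.4.1 says "The primary endpoint would then be a change in negative attention bias following training visits", and the next sentence reads "Phase R61 will focus on this negative attention bias, and Phase R33 will focus on change in depressive symptom severity". The Study Summary agrees: its R61 primary objective is to "compare the time spent in the most negative state before and after real-time neurofeedback training, comparing active vs sham training", and its R33 objective is the effect on depression.

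**Statements that use the word primary.** Section 5.1 has participants "screened using the MADRS, which will be the primary outcome measure and will have a minimum score of 16". Section 6.3.2, the one analysis headed as that of the primary outcome, reads in full: "We will use a two-sample t-test comparison of active neurofeedback vs sham to determine the effect on MADRS scores". Neither mentions a phase. Section 6.3.2 also gives no visit and does not choose between raw score and change.

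**R61 analyses elsewhere.** Section 6.1 gives detectable effects for a one-sample and a two-sample t-test with 27 per arm and cites a pilot effect on neural perseveration. Section 6.2 plans a mixed model in the active arm only, and active-versus-sham t-tests after each session. Both cover neural perseveration and MADRS. None is called primary. The between-arm neural comparison (R61 Aim 1) stands under the secondary headings in 2.2 and 3.4.2.

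**Neural variable.** The Study Summary uses time in the most negative state. Section 3.4.2 describes neural perseveration as a "higher conditional probability of staying in the same negative state vs. healthy individuals".

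**Gate.** Section 2.2 makes R33 depend on a successful R61 and does not define success.

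**The concern.** R61 is a randomised phase whose result decides whether a second trial is run. A reader should be able to say beforehand which variable, which contrast and which test decide it. Here the section headed as the primary analysis concerns a different outcome from the R61 endpoint. The analyses that do concern that endpoint form a list with none singled out. The variable itself can be computed in two ways that need not agree: a participant may enter the negative state often but leave quickly, or enter it rarely and stay.

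The success of R61 could therefore be claimed on whichever neural measure came out better, and nothing in the plan would contradict the claim. Section 6.2 assumes 5% error rates and states no adjustment for more than one test.

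**Working it through.** **1. The statements side by side.**

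| Place | R61 | R33 |
|---|---|---|
| Study Summary | Time in most negative state, active vs sham | Depression, active vs sham |
| 3.4.1 | Negative attention bias | Depressive symptom severity |
| 5.1 | MADRS (phase not stated) | MADRS (phase not stated) |
| 6.1 | One- and two-sample t-tests; pilot effect is on neural perseveration | MADRS decrease from Visit 1 to post-treatment; also change to 3 months |
| 6.2 | Neural perseveration and MADRS, after each session, plus active-arm model | Phase not stated |
| 6.3.2 | MADRS (phase not stated) | MADRS (phase not stated) |

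The Study Summary and 3.4.1 agree on the split. Sections 5.1 and 6.3.2 do not carry it, and no row supplies a single R61 test.

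**2. Is there an agreed post value for the neural measure?** Section 3.3 places the go/no-go task at the three training sessions and the post-training session. The visit table in 4.1, the table in section 5 and the text of 5.2.3 have no scan at the post-training visit. Section 3 counts four training sessions in R61 where the other places count three. A first-to-last training session contrast exists under each of these schedules; a contrast ending at the post-training visit does not.

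**3. The plan's own R61 detectable effects.** With two-sided 5%, 80% power and noncentral t:
- One-sample, n = 27: d = 0.56, as stated in 6.1.
- Two-sample, 27 per arm: d = 0.777, where 6.1 states 0.86. The noncentrality is d × √(27/2) = 0.777 × 3.674 = 2.85. Power at d = 0.86 is 87.3%.

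The stated 0.86 is reproduced at a two-sided alpha of 0.025 (d = 0.860). That would fit an unstated division of alpha over two tests, but the documents do not say so. At the stated 5% the figure is conservative.

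**4. Cost of leaving two neural measures open.** Under no effect, with each test two-sided at 5%:

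P(at least one significant) = 1 − P(|Z₁| ≤ 1.96 and |Z₂| ≤ 1.96)

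| Correlation of the two tests (assumed) | False-positive chance |
|---|---|
| 0 | 1 − 0.95² = 9.75% |
| 0.5 | 9.1% |
| 0.7 | 8.4% |
| 0.8 | 7.8% |

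The last three rows come from simulated correlated normal pairs. The documents give no correlation between the two measures. Two measures of the same brain state are likely to be well correlated, so 0.5 to 0.8 is used as the working range.

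**5. After the fix.** One neural between-arm test at two-sided 5% with 27 per arm detects d = 0.78 with 80% power. If the pilot's 0.83 carried over as a between-arm effect, power would be 84.9%. That is an assumption, because 6.1 sets 0.83 against the one-sample test.

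**The case against.** The strongest reply is that the plan resolves itself by phase. The Study Summary and 3.4.1 both assign the neural endpoint to R61 and symptoms to R33, so 5.1 and 6.3.2 can be read as R33 statements. Sections 6.1 and 6.2 show that a neural between-arm comparison in R61 was intended. The secondary heading over Aim 1 carries limited weight, since R33's depression comparison stands under the same heading. For R33, 6.1 already points to MADRS change to post-treatment.

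Much of this stands, and it rules out three stronger readings that a reader might infer.

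- *That R61's primary analysis would be run on MADRS.* Section 6.3.2 read alone allows this, but the Study Summary, 3.4.1 and 6.1 all make the R61 target neural.
- *That there are three rival neural measures, with 10–13% false positives.* Selective attention to negative stimuli is the aim-level construct. The same paragraph of 3.4.2 goes on to give neural perseveration as its proposed neural locus. Only two operational descriptions are established.
- *That free choice among five MADRS visits, at about 15%, measures the risk to the gate.* The count is uncertain: four to six visits are defensible, giving about 13% to 16% at an assumed correlation of 0.7. Section 3.4.2 bases the session choice on neural and behavioural markers, not MADRS. R33 also depends on approval.

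The reply does not supply a designated R61 test. Reading 5.1 and 6.3.2 as R33-only leaves R61 with no analysis headed as primary, two candidate variables, tests after each session and an undefined criterion for success.

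**Conclusion.** The point holds as a conflict between the stated endpoint and the text on the primary outcome. MADRS is called primary without limit to R33. R61 has planned neural between-arm tests, but none is designated as the one that decides the phase.

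Its size, for the choice between two neural measures alone, is a false-positive rate of about 8–9% instead of 5%. This rests on assumed correlations of 0.8 to 0.5 and on the better result being the one reported. It describes the room the plan leaves and does not predict how the investigators would act. It does not count the repeated testing by session in 6.2.

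Sample size is not at issue: 27 per arm is adequate for d = 0.86 at the stated 5%. Because R61 gates R33, this should be settled before any R61 outcome is compared between arms.

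**What to change.** 1. **Reconcile the schedule first.** Sections 3, 3.3, 4.1, the section 5 table and 5.2.3 must agree on the number of training sessions and on whether the go/no-go task is done at the post-training session. Section 5.2.1 mentions the baseline scans only for the active group, so the text should also state what is measured in the sham arm.
2. **R61, in 3.4.1 and 6.3.2.** Name one neural variable: either time in the most negative state or the neural perseveration probability. The second is the construct that 6.1 and 6.2 use and for which 6.1 gives a pilot effect. Name one pre-post contrast; first to last training session is available under every version of the schedule. Name one active-versus-sham test at two-sided 5% as primary.
3. **Gate, in 2.2.** Define a successful R61 by that test.
4. **MADRS, in 5.1 and 6.3.2.** Limit the primary statements to R33. Carry the post-treatment time point of 6.1 into 6.3.2 as the active-versus-sham comparison, adjusted for pre-training MADRS, which is already collected.
5. Label all other measures, sessions and visits secondary, in both phases.

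The cost is mostly wording, with no added visits or participants. The other measures can no longer carry the primary claim. The R33 t-test becomes a baseline-adjusted comparison, which is a change of method and should be recorded as one.
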